7.3. EXPAREL (bupivacaine liposome injectable suspension)

Bupivacaine is one of the longer-acting local anesthetics, but even so it has a limited duration of action after local administration, usually less than 8 hours. EXPAREL is a bupivacaine liposome injectable suspension. It consists of microscopic spherical, multivesicular liposomes (DepoFoam[®] drug delivery system), organized in a honeycomb-like structure comprising numerous non-concentric internal aqueous chambers containing a bupivacaine base at a concentration of 13.3 mg/mL. Each chamber is separated from adjacent chambers by lipid membranes. The lipids (phospholipids, cholesterol, and triglycerides) are naturally occurring or close analogs of endogenous lipids. Bupivacaine is slowly released from the DepoFoam particles by a complex mechanism involving reorganization of the barrier lipid membranes and subsequent diffusion of the drug over an extended period of time. EXPAREL has been noted in infiltration studies to have a bimodal curve (Apseloff 2013), with an initial peak occurring at approximately 0 to 2 hours and a second peak at approximately 24 to 48 hours (Hu 2013).

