13.1.7. Adverse Events of Special Interest

All AEs will be recorded from the time the ICF is signed/assent is given till Day 30. In case a cardiac or neurological AE of special interest (AESI) or serious AE (SAE) occurs during the study, if the investigator or medical monitor considers that the event may be related to study treatment or suggests the possible occurrence of local anesthetic systemic toxicity (LAST; with or without the need for treatment [e.g., intralipids]), or if a plausible etiology for the event cannot be found, an unscheduled PK blood sample must be collected and a 12-lead ECG, vital signs, and clinical laboratory tests (hematology and complete metabolic profile [CMP]) according to the study site's standard of care may be conducted. See Appendix 6 for additional information on handling of AESIs.

Cardiac AESIs include chest pain, abnormal/irregular heart rate, and shortness of breath requiring intervention. Neurologic AESIs include seizure, altered mental status/altered sensorium, rigidity, dysarthria, tremors, tinnitus, visual disturbance, and severe or worsening dizziness (see below). Additionally, the following events may be of special interest if they persist or occur beyond 72 hours post dose: dizziness, hyperesthesia, muscular twitching, and tingling/paresthesia.

Dizziness will be assessed as mild, moderate, or severe based on the NCI CTCAE Version 5.0. Mild dizziness is defined as mild unsteadiness or sensation of movement; moderate dizziness is defined as moderate unsteadiness or sensation of movement limiting instrumental ADL; and severe dizziness is defined as severe unsteadiness or sensation of movement that limits self-care ADLs. Dizziness will be captured as an AESI if it is severe or worsens or persist beyond 72 hours post dose. Cardiac or neurological AEs that do not meet one of these three criteria for AESI should be reported as described in Section 14.1 and captured in the database as an AE.

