6.7 Pharmacokinetic Analysis

6.7.1 Sample Collections for Pharmacokinetic Analysis

A sparse PK sampling scheme is used to limit the number of blood draws from individual subjects. On Day 1, eligible subjects will be assigned to one of two PK sampling groups shown in Table 2 based on surgery type. A total of 8 blood samples will be collected from each subject at the specific time windows shown for the determination of bupivacaine plasma concentrations.

Surgery	y PK Sample Timing (Based on the End of Study Drug Administration)							
Туре	Sample 1	Sample 2	Sample 3	Sample 4	Sample 5	Sample 6	Sample 7	Sample 8
Spine	15±5 min	30±5 min	45±5 min	1-1.25 h	2-3 h	10-18 h	24-36 h	42-60 h
Cardiac	15±5 min	30±5 min	45±5 min	1-1.25 h	15-25 h	30-40 h	45-55 h	64-72 h

Table 2PK Sampling Times

Abbreviations: h = hour; min = minutes; PK = pharmacokinetic

These sampling time points will not only characterize overall PK of bupivacaine from EXPAREL, but will also characterize the PK of immediate release bupivacaine and thoroughly characterize the early peak for both surgery types.

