6.7.2 Pharmacokinetic Parameters Calculation Methods

Nonsterospecific assay is used for the measurement of bupivacaine concentration. Pharmacokinetic parameters will be calculated by noncompartmental analysis (NCA) method from concentration-time data following these guidelines:

- Actual sampling times relative to study drug administration will be used for all calculations of the PK parameters. If there is any doubt as to the actual time a sample was taken, then the scheduled time will be used.
- Concentrations from unscheduled PK blood samples will be used in the analysis of the parameters.
- There will be no imputation of missing concentration data.
- For the summaries of concentrations and for calculation of area under the curve (AUC) from bupivacaine plasma concentrations, concentrations below the limit of quantification (BLOQ) will be handled as follows:
 - Pre-dose values will be set to zero.
 - BLOQ values between the dosing time and the first time point above lower limit of quantification (LLOQ) will be set to 0.
 - BLOQ values at time points between two measurable concentration values will be set to ½ of LLOQ (lower limit of quantification).
 - All remaining BLOQ values will be set to missing.

The following PK endpoints will be determined using non-compartmental methods:

- Area under the plasma concentration-versus-time curve (AUC0-∞ and AUC0-last). The AUC0-last from the time of dosing to the time of the last quantifiable concentration will be calculated using the linear trapezoidal method. The AUC0-∞ from the time of dosing (zero) to infinity will be calculated as sum of AUC0-last and residual area Ct/λz.
- Maximum plasma concentration (Cmax) and time of Cmax (Tmax).
- The apparent terminal elimination half-life (t1/2el). t1/2el will be calculated as $\log_e(2)/\lambda_z$. The apparent terminal elimination rate constant (λ_z) will be estimated at terminal phase by linear regression after log-transformation of the concentrations:
 - Only those data points that are judged to describe the terminal log-linear decline will be used in the regression.
 - A minimum number of three data points in the terminal phase will be used in calculating λ_z with the line of regression starting post the Cmax data point (Cmax will not be part of the regression slope) and including the last point above LLOQ value (Ct).
 - An appropriate number of decimal places will be used for λ_z to enable the reported value of terminal half-life (t1/2el) to be calculated.

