6.7.3 Pharmacokinetic Concentrations and Variables

A complete data listing will be provided for all PK bupivacaine concentration data. Concentrations that are BLOQ will be indicated in the listing.

A plot of bupivacaine concentration-time data, with original scale and semi-log scale overlain on the same page will be created for each individual subject.

If different than the preceding plot, a plot of dose-normalized concentration-time data, with the original scale and semi-log scale overlaid on same page, will also be created for each individual subject.

Plasma bupivacaine concentrations for each formulation will be summarized at each nominal time window (any out-of-window results would be shown only in a listing). The following descriptive statistics

will be presented: n, geometric mean, arithmetic mean, SD, %CV, median, minimum and maximum. Results will be summarized by treatment group (EXPAREL or bupivacaine HCl) for Group 1 and by surgery type (cardiac or spine) for Group 2. Plots of mean bupivacaine concentration over time will be created with the original scale and semi-log scale overlain on the same page. If the number of subjects in a group is less or equal to 3, then individual concentration over time curves will be plotted instead of the mean concentration. For group 1, there will be two plots overlain for the two treatments. For group 2, there will be two separate plots for the two types of surgery.

Pharmacokinetics parameters will be presented in the data listings and descriptive summary statistics, including the arithmetic mean, median, minimum, maximum, standard deviation, %CV of mean, geometric mean, %CV of geometric mean. Differences will be compared between the two formulations using single factor ANOVA.

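### Group 1 NCA half-life, AUC0-inf, CL/F and Vd/F would be tested between formulations only in subjects with an estimable lambda_z, a subset that randomization does not protect (minor)

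*SAP*

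**What the plan says.** SAP 6.7.2 introduces its parameter list with "The following PK endpoints will be determined using non-compartmental methods" and adds population PK modelling as a further analysis. For the terminal slope it states "A minimum number of three data points in the terminal phase will be used in calculating" lambda_z. The regression starts after the Cmax point, leaves that point out, ends at the last quantifiable concentration, and uses only points judged to lie on the terminal log-linear decline. Missing concentrations are not imputed, and trailing values below the limit of quantification are set to missing. On extra samples the SAP says "Concentrations from unscheduled PK blood samples will be used in the analysis of the parameters".

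SAP 6.7.1 gives eight scheduled samples. On the spine schedule, which applies to every Group 1 PK subject, the last three are at "10-18 h 24-36 h 42-60 h".

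SAP 6.7.3 then says "Differences will be compared between the two formulations using single factor ANOVA". The Table 14.4-1.1 shell prints p-value rows for AUC(0-inf) and AUC(0-last) with a two-sided t-test footnote, and extends the same template to Cmax, Tmax, t1/2el, CL/F and Vd.

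Protocol 12.2 defines the PK endpoints as model-predicted. Protocol 15.1 plans no formal hypothesis testing, and 15.7 marks significance testing as not applicable. SAP 6.11 declares the NCA as an addition to the protocol but does not mention the tests. Protocol 7.3 describes an EXPAREL profile "with an initial peak occurring at approximately 0 to 2 hours and a second peak at approximately 24 to 48 hours".

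**The concern.** The three-point rule is a sound safeguard against a poorly determined slope. The difficulty is a p-value computed only on those who pass it. Whether a subject passes depends on the concentration profile after dosing: where the maximum falls, whether late samples are quantifiable, and whether the tail is log-linear. The formulation can influence all three. Protocol 7.3 describes a late second peak for EXPAREL, so loss that differs by arm is foreseeable. Subjects with an estimable lambda_z in the two arms are then no longer the groups that were randomized. A difference, or its absence, in half-life, AUC0-inf, clearance or volume could partly reflect who remained. The comparison is also one that the protocol did not plan.

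**Working it through.** **Inputs.** Part 1 Group 1 has 30 subjects, all spine surgery, randomized 1:1 (15 + 15 = 30; SAP 3). There are eight scheduled samples (SAP 6.7.1) and at least three points are needed after Cmax (SAP 6.7.2). The sample size rests on PK precision, with no variance or precision target given (SAP 6.10.1), so it cannot be re-derived.

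**Step 1: scheduled points left.** With Cmax at sample k, 8 - k scheduled points remain. If sample 8 is missing or not quantifiable, 7 - k remain.

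| Cmax at (spine) | Points left | If sample 8 is lost |
|---|---|---|
| 15 min | 7 | 6 |
| 30 min | 6 | 5 |
| 45 min | 5 | 4 |
| 1-1.25 h | 4 | 3 |
| 2-3 h | 3 | 2 |
| 10-18 h | 2 | 1 |
| 24-36 h | 1 | 0 |
| 42-60 h | 0 | - |

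The rule can be met up to a Cmax at 2-3 h, or only up to 1-1.25 h if the last sample drops out.

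**Step 2: the log-linear condition.** An early Cmax does not guarantee a slope. If a second rise tops out at the 24-36 h sample, at most two scheduled points (24-36 h and 42-60 h) lie on the final decline.

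**Step 3: what depends on lambda_z** (SAP 6.7.2).
- t1/2el = ln(2)/lambda_z
- AUC0-inf = AUC0-last + Ct/lambda_z
- CL/F = Dose/AUC0-inf
- Vd/F = Dose/(lambda_z x AUC0-inf)

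All four are lost together. Cmax, Tmax and AUC0-last do not use lambda_z.

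**Step 4: size, over an assumed range.** The share p of EXPAREL subjects with Cmax at sample 6 or later is not in the documents. Expected evaluable = 15(1 - p). The chance that all 15 remain = (1 - p)^15.

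| Assumed p | Expected evaluable | Binomial 95% range | All 15 remain |
|---|---|---|---|
| 5% | 14.3 | 12-15 | 46% |
| 10% | 13.5 | 11-15 | 21% |
| 25% | 11.3 | 8-14 | 1.3% |
| 50% | 7.5 | 4-11 | 0.003% |
| 75% | 3.8 | 1-7 | about 0 |

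**Step 5: possible shift, over an assumed range.** Suppose only EXPAREL loses subjects, and the parameter has normal correlation rho with peak timing. The evaluable mean then shifts by rho x phi(z)/(1 - p) SD, with z the normal quantile of 1 - p. The standard error (SE) of the difference is sqrt(1/15 + 1/(15(1 - p))) SD.

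| Assumed p | Shift, abs(rho) = 0.3 | Shift, abs(rho) = 0.6 | SE of difference |
|---|---|---|---|
| 10% | 0.06 | 0.12 | 0.38 |
| 25% | 0.13 | 0.25 | 0.39 |
| 50% | 0.24 | 0.48 | 0.45 |
| 75% | 0.38 | 0.76 | 0.58 |

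At rho = 0 the shift is zero. Otherwise it can go either way. It stays below one SE at 10-25% loss, and reaches about one SE at 50% loss only with the stronger correlation.

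**The case against.** Several points on the other side are good.

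- **Tmax is not the sole selector.** A reader might infer that the tested subset is picked by Tmax alone, or that only EXPAREL subjects drop out. The documents do not support that. The log-linear judgement can exclude subjects with an early Cmax, and trailing unquantifiable values could remove bupivacaine HCl subjects.
- **The harm is conditional.** Protocol 7.3 does not say which EXPAREL peak is higher, so late maxima may be rare. The shares and correlations above are assumptions, and over much of the range the shift is small beside the SE. This stands.
- **The loss is already visible.** Table 14.4-1.1 shows N by arm and n for each parameter, so N minus n gives the count. Tmax is on the same table, the listing defines ND, and individual profiles are plotted. Only the reason is missing.
- **The primary objective does not rest on the NCA.** Protocol 12.2 makes the endpoints model-predicted, SAP 6.11 calls the NCA additional, and the population model uses all PK data. The objective is to describe EXPAREL, not to compare formulations.
- **Unscheduled samples count.** They could rescue a subject, but the protocol's requirement that "an unscheduled PK blood sample must be collected" applies only around qualifying events of special interest or serious adverse events (13.1.7).

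What these points do not answer is the p-value itself. Showing n and ND labels the loss but does not turn a comparison of the remaining subjects into a randomized one.

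**Conclusion.** The point holds, at minor severity. The counts in Steps 1 and 3 are exact: with a Cmax at 10-18 h or later, the rule cannot be met from scheduled samples in Group 1, and four NCA parameters then become non-estimable together. The planned tests of those parameters apply to a subset defined by the post-dose profile, and neither the protocol nor SAP 6.11 provides for them. How many subjects are lost, in which arm, and with what bias are all unknown; Steps 4 and 5 are ranges under stated assumptions, not predictions.

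A reader might go further and conclude that the primary PK result is biased, or that EXPAREL exposure will be misstated in a known direction. Neither follows. The population PK analysis, Cmax, Tmax and AUC0-last are not affected by this selection, and the documents give no direction. The cardiac schedule does not bear on the test either, because Group 2 is single-arm.

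**What to change.** Remove the between-formulation p-values for NCA t1/2el, AUC0-inf, CL/F and Vd/F from SAP 6.7.3 and Table 14.4-1.1. Report these parameters descriptively, with n by arm as the shell already shows. Whether Cmax, Tmax and AUC0-last should keep a p-value, given protocol 15.1 and 15.7, is a separate question to settle at the same time, so that the table is consistent.

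Two optional clarifications:
- State in SAP 6.7.2 or 6.11 that the model-predicted values of protocol 12.2 answer the primary objective and that the lambda_z-dependent NCA values are supportive.
- Give the reason for each ND value (late Cmax, missing or below quantification, not log-linear).

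The cost is SAP wording and table shells, with no new samples, subjects or models. One consequence of the first clarification is that the main values of these four parameters would be read from the separate population PK report (protocol 15.6.3) rather than from this SAP's tables.

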6.7.3 Pharmacokinetic Concentrations and Variables

A complete data listing will be provided for all PK bupivacaine concentration data. Concentrations that are BLOQ will be indicated in the listing.

A plot of bupivacaine concentration-time data, with original scale and semi-log scale overlain on the same page will be created for each individual subject.

If different than the preceding plot, a plot of dose-normalized concentration-time data, with the original scale and semi-log scale overlaid on same page, will also be created for each individual subject.

Plasma bupivacaine concentrations for each formulation will be summarized at each nominal time window (any out-of-window results would be shown only in a listing). The following descriptive statistics

will be presented: n, geometric mean, arithmetic mean, SD, %CV, median, minimum and maximum. Results will be summarized by treatment group (EXPAREL or bupivacaine HCl) for Group 1 and by surgery type (cardiac or spine) for Group 2. Plots of mean bupivacaine concentration over time will be created with the original scale and semi-log scale overlain on the same page. If the number of subjects in a group is less or equal to 3, then individual concentration over time curves will be plotted instead of the mean concentration. For group 1, there will be two plots overlain for the two treatments. For group 2, there will be two separate plots for the two types of surgery.

Pharmacokinetics parameters will be presented in the data listings and descriptive summary statistics, including the arithmetic mean, median, minimum, maximum, standard deviation, %CV of mean, geometric mean, %CV of geometric mean. Differences will be compared between the two formulations using single factor ANOVA.

